10.1.1.2. Treatment groups

Treatment considered for the analysis of Safety Lead-In part will be the following:

- Futuximab/modotuximab + trifluridine/tipiracil.

Treatment groups considered for the analysis of Randomised part will be the following:

- Futuximab/modotuximab + trifluridine/tipiracil (Arm A).
- Trifluridine/tipiracil (Arm B).

10.1.2. Statistical methods

10.1.2.1. General considerations

The data from Safety Lead-In part and Randomised part will be summarized, analysed and listed separately.

The following descriptive statistics will be provided depending on the nature of considered data:

- Qualitative data: number of observed values, number and percentage of participants per class.
- Quantitative data: number of observed values, mean and standard deviation, median, first and third quartiles, minimum and maximum.
- Survival data (time to event occurrence or to censoring): total number of participants, total number and percentage of participants having an event overall, number of participants at risk, number of participants with censored data, number of participants with event of interest.

10.1.2.2. Disposition and baseline characteristics

The participants' disposition and baseline characteristics will be described in SS for Safety Lead-In part and in the FAS by treatment arms and overall for Randomised part.

The number of participants in each study population and the reasons for exclusion, along with any randomisation and/or stratification errors will be summarized as well as the disposition of participants, including reasons for discontinuation and protocol deviations at baseline and during study.

Characteristics of participants including demography, characteristics of the disease at diagnosis and study entry, medical history, prior therapy and concomitant medication at baseline will be summarised.

10.1.2.3. Treatments of participants

Extent of exposure and treatment compliance, as well as concomitant medication during treatment period will be described in the SS. Extent of exposure includes number of cycles, cumulative dose, dose intensity, relative dose intensity, dose modifications.

The follow-up duration will be calculated overall and in each arm with the reverse Kaplan-Meier method.

The non-study cancer treatment after study treatment discontinuation will be summarized. Any use of non-study cancer treatment during the study treatment period will also be presented as protocol deviation.

10.1.2.4. Efficacy analysis

10.1.2.4.1. Safety Lead-In part

The proportion of participants with objective evidence of CR or partial response (PR) (ORR) according to RECIST version 1.1 criteria and using investigator's tumour assessment will be summarized descriptively.

The proportion of participants with BOR according to RECIST version 1.1 criteria and using investigator's tumour assessment will be summarized descriptively.

The proportion of participants with objective evidence of CR or PR or stable disease (SD) (DCR) according to RECIST version 1.1 criteria and using investigator's tumour assessment will be summarized descriptively.

PFS is defined as the time from the first administration of IMP date until the date of the investigator-assessed radiological disease progression according to RECIST version 1.1 or death, whichever occurs first. PFS will be summarized using Kaplan Meier curve and further characterised in terms of the median and survival probabilities at 2, 4, 6 and 8 months along with the corresponding 2-sided 95% CI for the estimates.

OS is defined as the time from the first administration of IMP date until the date of death due to any cause. OS will be summarized using Kaplan Meier curve and further characterised in terms of the median and survival probabilities at 6, 12 and 18 months along with the corresponding 2-sided 95% CI for the estimates.

10.1.2.4.2. Randomised Part

Primary objective

The primary objective is to demonstrate the superiority of futuximab/modotuximab in combination with trifluridine/tipiracil over trifluridine/tipiracil monotherapy in terms of OS in participants with chemotherapy pre-treated (including oxaliplatin, irinotecan and 5-fluorouracil, anti-VEGF agents, and anti-EGFR mAb therapy for ≥ 16 weeks) metastatic colorectal cancer that are KRAS/NRAS and BRAF WT (Double negative [DN]).

Key secondary objective

The key secondary objective is to demonstrate the superiority of futuximab/modotuximab in combination with trifluridine/tipiracil over trifluridine/tipiracil monotherapy in terms of OS in participants with chemotherapy pre-treated (including oxaliplatin, irinotecan and 5-fluorouracil, anti-VEGF agents, and anti-EGFR mAb therapy for ≥ 16 weeks) metastatic colorectal cancer that are KRAS/NRAS, BRAF WT and EGFR-extracellular domain WT (Triple negative [TN]).

Secondary objectives

Secondary objectives are to estimate the effect of futuximab/modotuximab in combination with trifluridine/tipiracil *versus* trifluridine/tipiracil monotherapy in terms of PFS, OR, DC, DoR, TTNT, TTR, and TtPS2 in participants with chemotherapy pre-treated (including oxaliplatin, irinotecan and 5-fluorouracil, anti-VEGF agents, and anti-EGFR mAb therapy for ≥ 16 weeks) metastatic colorectal cancer.

Other secondary objectives are to compare the safety and tolerance, and the impact on QoL of futuximab/modotuximab in combination with trifluridine/tipiracil to trifluridine/tipiracil monotherapy in participants with chemotherapy pre-treated metastatic colorectal cancer.

Intercurrent events

During the study the following intercurrent events could occur:

- Administration of further anti-cancer therapy.
- Treatment discontinuation.
- Treatment switch (from futuximab/modotuximab in combination with trifluridine/tipiracil to trifluridine/tipiracil monotherapy and from trifluridine/tipiracil monotherapy to futuximab/modotuximab in combination with trifluridine/tipiracil).

Estimands of interest

The attribute treatment will be the same for all estimands of interest:

- Treatment: Futuximab/modotuximab + trifluridine/tipiracil *versus* trifluridine/tipiracil monotherapy.

The following estimands will be studied:

Table (10.1.2.4.2) 1 - Studied estimands

Estimand	Variable	Population level summary	Handling intercurrent events (IEs)	Population
Primary estimand: effect of the randomised treatments on the survival duration in all subjects that are KRAS/NRAS and BRAF WT (Double negative [DN]) regardless of whether or not intercurrent events occur	OS	HR	Treatment policy strategy	FAS
Key secondary estimand: effect of the randomised treatments on the survival duration in all subjects that are KRAS/NRAS, BRAF WT and EGFR-extracellular domain WT (Triple negative [TN]) regardless of whether or not intercurrent events occur	OS	HR	Treatment policy strategy	FAS restricted to Triple negative [TN] subjects
Effect of the randomised treatments on the survival duration in all subjects that are KRAS/NRAS and BRAF WT (Double negative [DN]) before participants receive further anti-cancer therapy	OS	HR	While on treatment strategy	FAS
Effect of the randomised treatments on the survival duration in all subjects that are KRAS/NRAS, BRAF WT and EGFR-extracellular domain WT (Triple negative [TN]) before participants receive further anti-cancer therapy	OS	HR	While on treatment strategy	FAS restricted to Triple negative [TN] subjects
Effect of the randomised treatments on progression-free survival before participants receive further anti-cancer therapy	PFS	HR	While on treatment strategy	FAS
Effect of the randomised treatments on progression-free survival regardless of whether or not intercurrent events occur	PFS	HR	Treatment policy strategy	FAS
Effect of the randomised treatments on response before participants receive further anti-cancer therapy	OR DC	Risk difference	While on treatment strategy	FAS

Table (10.1.2.4.2) 1 (Cont'd) - Studied estimands

Estimand	Variable	Population level summary	Handling intercurrent events (IEs)	Population
Effect of the randomised treatments on the response duration before participants receive further anti-cancer therapy	DoR	HR	While on treatment strategy	FAS
Effect of the randomised treatments on the time from the randomisation to initiation of the next systemic anti-cancer therapy	TTNT	HR	While on treatment strategy	FAS
Effect of the randomised treatments on the time from randomisation until first radiologically confirmed tumour response (CR or PR) before participants receive further anti-cancer therapy	TTR	HR	While on treatment strategy	FAS
Effect of the randomised treatments on the time from the date of randomisation to the date when ECOG PS score of ≥ 2 is observed for the first time before participants receive further anti-cancer therapy	TtPS2	HR	While on treatment strategy	FAS

With:

- OS: overall survival defined as the time from date of randomisation into the study to death from any cause.
- PFS: progression-free survival defined as the time from date of randomisation until the date of the investigator-assessed radiological disease progression or death, whichever occurs first.
- OR: overall response defined as the achievement of confirmed CR or PR according to RECIST version 1.1 criteria and using investigator's tumour assessment.
- DC: disease control defined as the achievement of best response of CR or PR or SD according to RECIST version 1.1 criteria and using investigator's tumour assessment.
- DoR: duration of response defined as the time from the first documentation of confirmed tumour response (CR or PR) according to RECIST version 1.1 criteria and using investigator's tumour assessment to the first documentation of objective tumour progression or to death due to any cause.
- TTNT: time to next treatment defined as the time from the randomisation to initiation of the next systemic anti-cancer therapy.
- TTR: time to response defined as the time from randomisation until first radiologically confirmed tumour response (CR or PR) according to RECIST version 1.1 criteria and using investigator's tumour assessment.
- TtPS2: time to ECOG performance status ≥ 2 defined as the time from the date of randomisation to the date when ECOG PS score of ≥ 2 is observed for the first time.

Estimands and the way for handling IEs will be detailed in the following paragraphs.

10.1.2.4.2.1. Primary estimand based on the OS

The primary estimand of interest is the effect of the randomised treatments on the survival duration in all subjects that are KRAS/NRAS and BRAF WT (Double negative [DN]) regardless of whether or not intercurrent events occur (treatment policy strategy). The motivation for this choice is to assess the efficacy of the futuximab/modotuximab in combination with trifluridine/tipiracil compared to trifluridine/tipiracil monotherapy under the ITT principle (intercurrent events are considered to be part of the treatments being compared).

All data collected during the trial regardless of occurrence of an IE will be used. This is aligned with the treatment policy strategy.

Primary analysis

The distribution of OS will be compared between the two treatment groups using a stratified log-rank test at one-sided 2.5% level of significance (stratification factors based on IWRS data).

OS for each arm will be summarized using Kaplan Meier curves and further characterised in terms of the median and survival probabilities at 6, 12 and 18 months along with the corresponding 2-sided 95% CI for the estimates.

The hazard ratio of OS with its 95% confidence interval will be estimated with a stratified Cox proportional hazard model (stratification factors based on IWRS data).

For missing data (not linked to intercurrent events), *i.e.* participants without documentation of death (lost to follow-up, withdrawal of consent, administrative end of study), the OS will be censored on the last contact date the participant was known to be alive or the cut-off date, whichever is earlier.

Sensitivity analyses

As sensitivity analyses, the following analyses will be done:

- The proportional hazards assumption will be checked. If relevant, other statistical method could be used.
- OS analysis based on PPS.

Other sensitivity analyses will be defined in the SAP if necessary.

Supplementary analyses

Subgroup analyses

OS subgroup analyses are planned to further explore the homogeneity of the treatment effect across participant subsets. Depending on the sample size, the following subgroups will be examined: ECOG PS (0, 1), extracellular domain EGFR mutations (ECD) (presence, absence), previous regimens of treatment (2, \geq 3), region (North America, European Union, Asia, Rest of the World), time since diagnosis of 1st metastasis (< 18, \geq 18 months), location of primary disease (right, left), gender (female, male), age (< 70, \geq 70 years), prior surgical resection (yes, no), number of metastatic sites (1-2, \geq 3), neutrophils to lymphocytes ratio (NLR < 3, NLR \geq 3), neutrophils to lymphocytes ratio (NLR < 5, NLR \geq 5), response to previous treatment with anti-EGFR (CR/PR, SD), last previous regimen (anti-EGFR, no anti-EGFR), previously treated with anti-VEGFs treatment (yes, no), skin toxicity with previous anti-EGFR (yes, no), skin toxicity with previous anti-EGFR (Grade 1-2, Grade 3-4, no toxicity), duration of previous anti-EGFR (< 8, \geq 8 months), Race (White, American Indian/Alaska native, Asian, Black/African

American, Native Hawaiian/Other pacific islander), Premedication with antibiotics for skin toxicity (yes, no).

A stratified Cox-regression model with treatment arm as predictor variable will be fitted separately for each subgroup category. The hazard ratio for treatment along with the associated 95% confidence interval will be provided.

Exploratory analysis

A multivariate OS analysis will be performed using a stratified Cox proportional hazard model (3 stratification factors (ECOG PS (0 *versus* 1), extracellular domain EGFR mutations (ECD) (presence *versus* absence) and previous regimens of treatment (2 *versus* ≥ 3)). Treatment will be included in the model and a stepwise selection process (p-value to enter < 0.15 , p-value to remain < 0.10) will be applied to identify potential additional prognostic factors among the following covariates: region (North America, European Union, Asia, Rest of the World), time since diagnosis of 1st metastasis (< 18 , ≥ 18 months), location of primary disease (right, left), gender (female, male), age (< 70 , ≥ 70 years), prior surgical resection (yes, no), number of metastatic sites (1-2, ≥ 3), neutrophils to lymphocytes ratio (NLR < 3 , NLR ≥ 3), neutrophils to lymphocytes ratio (NLR < 5 , NLR ≥ 5), response to previous treatment with anti-EGFR (CR/PR, SD), last previous regimen (anti-EGFR, no anti-EGFR), previously treated with anti-VEGFs treatment (yes, no), skin toxicity with previous anti-EGFR (yes, no), skin toxicity with previous anti-EGFR (Grade 1-2, Grade 3-4, no toxicity), duration of previous anti-EGFR (< 8 , ≥ 8 months), Race (White, American Indian/Alaska native, Asian, Black/African American, Native Hawaiian/Other pacific islander), Premedication with antibiotics for skin toxicity (yes, no).

10.1.2.4.2.2. Key secondary estimand based on the OS

The key secondary estimand of interest is the effect of the randomised treatments on the survival duration in all subjects that are KRAS/NRAS, BRAF WT and EGFR-extracellular domain WT (Triple negative [TN]) regardless of whether or not intercurrent events occur (treatment policy strategy). The motivation for this choice is to assess the efficacy of the futuximab/modotuximab in combination with trifluridine/tipiracil compared to trifluridine/tipiracil monotherapy under the ITT principle (intercurrent events are considered to be part of the treatments being compared).

All data collected during the trial regardless of occurrence of an IE will be used. This is aligned with the treatment policy strategy.

The following analyses will be done as primary analyses:

- The distribution of OS will be compared between the two treatment groups using a stratified log-rank test at one-sided 2.5% level of significance (stratification factors based on IWRS data).
- OS for each arm will be summarized using Kaplan Meier curves and further characterised in terms of the median and survival probabilities at 6, 12 and 18 months along with the corresponding 2-sided 95% CI for the estimates.
- The hazard ratio of OS with its 95% confidence interval will be estimated with a stratified Cox proportional hazard model (stratification factors based on IWRS data).

As OS in TN population is identified as the key secondary estimand, closed sequential testing procedure will be used to statistically evaluate and interpret OS in TN population only if the

primary estimand, OS in DN population, is statistically significant. Therefore, the family-wise error rate is strongly controlled.

The following analyses will be done as sensitivity analyses:

- The proportional hazards assumption will be checked. If relevant, other statistical method could be used.
- OS analysis based on PPS.

Other sensitivity analyses will be defined in the SAP if necessary.

For missing data (not linked to intercurrent events), *i.e.* participants without documentation of death (lost to follow-up, withdrawal of consent, administrative end of study), the OS will be censored on the last contact date the participant was known to be alive or the cut-off date, whichever is earlier.

The same subgroup analyses as used for the primary estimand will be done.

10.1.2.4.2.3. Supplementary estimand based on OS

One supplementary estimand based on OS is defined in order to assess the effect of the randomised treatments on the survival time in all subjects who are KRAS/NRAS and BRAF WT (Double negative [DN]) before participants receive further anti-cancer therapy (while on treatment strategy).

The other estimand based on OS is defined in order to assess the effect of the randomised treatments on the survival time in all subjects who are KRAS/NRAS, BRAF WT and EGFR-extracellular domain WT (Triple negative [TN]) before participants receive further anti-cancer therapy (while on treatment strategy).

The aim of this estimand is to evaluate the effect of the study treatment without a potential effect of another therapy.

The use of data post intercurrent events will be different according to the IE:

- For IE “administration of further anti-cancer therapy” and “treatment switch”: data obtained post IE will not be used for the analysis. OS will be censored at the time of administration of further anti-cancer therapy.
- For IE “treatment discontinuation”: time of death for any cause after treatment discontinuation will be taken into account.

These strategies are aligned with those estimands.

The distribution of OS will be compared between the two treatment groups using a stratified log-rank test at one-sided 2.5% level of significance (stratification factors based on IWRS data).

For missing data (not linked to intercurrent events), *i.e.* participants without documentation of death (lost to follow-up, withdrawal of consent, administrative end of study), the OS will be censored on the last contact date the participant was known to be alive or the cut-off date, whichever is earlier.

Other estimands will be defined in the SAP if necessary.

10.1.2.4.2.4. Secondary estimands based on PFS, OR, DC, DoR, TTNT, TTR and TtPS2

Secondary estimand based on PFS

One secondary estimand of interest is the effect of the randomised treatments on progression-free survival in all subjects before participants receive further anti-cancer therapy (while on treatment strategy). For participants who start the subsequent anti-cancer therapy before disease progression or death will be censored at the date of last evaluable tumour assessment prior to the date of any subsequent anti-cancer therapy. This is aligned with the estimand and the while on treatment strategy.

The other secondary estimand of interest is the effect of the randomised treatments on progression-free survival in all subjects regardless of whether or not intercurrent events occur (treatment policy strategy). All data collected during the trial regardless of occurrence of an IE will be used. This is aligned with the treatment policy strategy.

The following analyses will be done as primary analyses:

- The distribution of PFS will be compared between the two treatment groups using a stratified log-rank test at one-sided 2.5% level of significance (stratification factors based on IWRS data).
- PFS for each arm will be summarized using Kaplan Meier curves and further characterised in terms of the median and survival probabilities at 2, 4, 6 and 8 months along with the corresponding 2-sided 95% CI for the estimates.
- The hazard ratio of PFS with its 95% confidence interval will be estimated with a stratified Cox proportional hazard model (stratification factors based on IWRS data).

The following analyses will be done as sensitivity analyses:

- An analysis that considers clinical progression and administration of further anti-cancer therapy as PFS events in addition to the radiological progression or death.
- PFS analysis based on PPS.

For missing data (not linked to intercurrent events), *i.e.* participants who were lost to follow-up or who have withdrawn their consent without radiological progression or reached the time point of analysis without a known record of death or radiological progression, the PFS will be censored at the date of last evaluable tumour assessment or the cut-off date, whichever is earlier.

The same subgroup analyses as used for the primary estimand will be done for PFS.

Secondary estimands based on ORR and DCR

Other secondary estimand of interest are the effect of the randomised treatments on response in all subjects before participants receive further anti-cancer therapy.

Responses recorded after intercurrent event will be excluded. This is aligned with the estimand and the treatment while on treatment strategy.

The following analyses will be done:

- OR based on the investigator's tumour assessment will be compared in the FAS between treatment arms using a stratified Cochran-Mantel-Haenszel (CMH) test. A 2-sided 95% CI for the difference in ORR between the two treatment arms will also be provided based on the normal approximation. If required, a Fisher's exact test and 2-sided 95% Clopper-

Pearson CIs will be used. A 2-sided 95% CI for the difference in ORR between the two treatment arms will also be provided based on the normal approximation.

- DC based on the investigator's tumour assessment will be compared in the FAS between treatment arms using a stratified CMH test. A 2-sided 95% CI for the difference in DCR between the two treatment arms will also be provided based on the normal approximation. If required, a Fisher's exact test and 2-sided 95% Clopper-Pearson CIs will be used. A 2-sided 95% CI for the difference in DCR between the two treatment arms will also be provided based on the normal approximation.

Secondary estimands based on DoR, TTNT, TTR and TtPS2

Responses recorded after intercurrent event will be excluded. This is aligned with the estimand and the treatment while on treatment strategy.

The following analyses will be done:

- The distribution of DoR per investigator's tumour assessment will be compared between the two treatment groups using a stratified log-rank test at one-sided 2.5% level of significance (stratification factors based on IWRS data).
- DoR per investigator's tumour assessment for each arm will be summarized using Kaplan Meier curves and further characterised in terms of the median along with the corresponding 2-sided 95% CI for the estimate.
- The distribution of TTNT will be compared between the two treatment groups using a stratified log-rank test at one-sided 2.5% level of significance (stratification factors based on IWRS data).
- TTNT for each arm will be summarized using Kaplan Meier curves and further characterised in terms of the median along with the corresponding 2-sided 95% CI for the estimate.
- The distribution of TTR per investigator's tumour assessment will be compared between the two treatment groups using a stratified log-rank test at one-sided 2.5% level of significance (stratification factors based on IWRS data).
- TTR per investigator's tumour assessment for each arm will be summarized using Kaplan Meier curves and further characterised in terms of the median along with the corresponding 2-sided 95% CI for the estimate.
- The distribution of TtPS2 will be compared between the two treatment groups using a stratified log-rank test at one-sided 2.5% level of significance (stratification factors based on IWRS data).
- TtPS2 for each arm will be summarized using Kaplan Meier curves and further characterised in terms of the median along with the corresponding 2-sided 95% CI for the estimate.

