2.8. Known Risks of the Therapeutic Regimen

In the dose-expansion part of the Phase 1 Sym004-01 study, 20 patients with heavily pre-treated mCRC were treated with the 9/6 regimen of futuximab/modotuximab. All 20 patients experienced an AE of “skin and subcutaneous disorders” (58 AEs in 20 patients, 100.0%). The most frequently experienced AEs in this system organ class (SOC) were rash (18 patients, 90.0%) and skin fissures (10 patients, 50.0%). Additionally, 18 events of hypomagnesemia (11 patients, 55.0%), were reported.

In the randomised Phase 2 Sym004-05 study, a total of 84 pre-treated mCRC patients were included in the 9/6 arm. A total of 78 patients (93%) experienced an AE of “dermatological toxicity”, while 47 patients (56%) were reported with any Grade of hypomagnesemia AE. Additional details are provided in the futuximab/modotuximab Investigator’s Brochure.

Neither dermatological toxicity, nor hypomagnesemia are reported as common toxicities of single-agent trifluridine/tipiracil; the most frequently observed adverse drug reactions ($\geq 30\%$) in patients receiving trifluridine/tipiracil are neutropenia (53% [34% \geq Grade 3]), nausea (34% [1% \geq Grade 3]), fatigue (32% [4% \geq Grade 3]) and anaemia (32% [12% \geq Grade 3]).⁸

The study will be conducted in compliance with the protocol, Good Clinical Practice (GCP), the ethical principles that have their origin in the Declaration of Helsinki [Appendix 1](#) and the applicable regulatory requirements.

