4.1.1. Study plan

This is a randomised, open label, multi-centre, two-arm Phase 3 study to evaluate futuximab/modotuximab in combination with trifluridine/tipiracil *versus* trifluridine/tipiracil monotherapy in participants ≥ 18 years of age with KRAS/NRAS and BRAF WT mCRC who were previously treated with chemotherapy (including oxaliplatin, irinotecan and 5-fluorouracil, anti-VEGF agents) and with anti-EGFR mAb therapy for ≥ 16 weeks.

The study will comprise two parts a Safety Lead-In part in approximately 25 participants and a Randomised part in approximately 500 participants.

The study design is depicted in [Figure \(4.1.1\) 1](#).

Figure (4.1.1) 1 - CL3-95026-001 Study Design

AE = adverse event; DLT = dose-limiting toxicity; ECD = extracellular domain; EGFR = epidermal growth factor receptor; mCRC = metastatic colorectal cancer; TEAE = treatment-emergent adverse event; STEAE = serious treatment emergent adverse events

Figure (4.1.1) 2 - Study plan for the Safety Lead-In Part

[figure not shown]
[figure not shown]

Figure (4.1.1) 3 - Study plan for the Randomised part

The study start is defined as the date of the first visit of the first participant.

The study will be divided into the following periods for each participant:

- Screening visit/Screening period (maximum 28 days):
 - Screening visit: after signature of the Informed Consent Form(s) (ICF) to check screening criteria and decide if participant can be screened for the study.
 - Screening period: if the participant is screened in the study, check the inclusion and exclusion criteria and decide if participant can be included in the study.
 - Randomisation: included participants will be randomly assigned to one of the two treatment groups:
 - Arm A: trifluridine/tipiracil + futuximab/modotuximab.
 - Arm B: trifluridine/tipiracil.
- Treatment period: participants will be treated until they meet a discontinuation criterion as described in [Section 5.8.1](#). The participants should receive the first dose of first IMP (Day 1 of Cycle 1) within 3 days after inclusion (in the Safety Lead-in part) or after randomisation.
- Withdrawal visit (WV): should be conducted within approximately 4 weeks following the date of study treatment withdrawal and before the start of a new anticancer therapy.
- Follow-up period: after the WV the participant will be followed every 8 weeks (\pm 10 calendar days):

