6.1.2. Premedication before futuximab/modotuximab administration

6.1.2.1. Premedication for Infusion-Related Reactions

6.1.2.1.1. Infusion-Related Reactions

There is an inherent risk for infusion-related reactions (IRRs) with the administration of mAbs. An IRR is defined as an AE occurring during the futuximab/modotuximab infusion and up to 24 hours after the end of infusion (EoI), which is assessed by the investigator to be related to the infusion. Signs and symptoms of IRRs may include but are not limited to:

- Facial flushing and swelling.
- Rash including urticaria.
- Headache.
- Fever.
- Chills, rigors.
- Diaphoresis.
- Tachycardia.
- Hypotension.
- Nausea.
- Dry mouth.
- Chest/back/abdominal pain/discomfort.
- Chest and throat tightness.
- Shortness of breath.
- Cough, wheeze, stridor.
- Hypoxia.
- Bronchospasm.
- Laryngeal edema.
- Angioedema.
- Shock.

The risk of an IRR is highest for the first administration of a mAb and diminishes with subsequent infusions. If an IRR occurs, it should be classified according to the NCI-CTCAE v5.0.

Guidelines for grading and management of IRRs of all severities are provided ([Appendix 9](#)).

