6.1.2.2. Premedication for skin toxicity

Management of skin toxicity will be done throughout the study according to the investigator's discretion. PABA free SPF \geq 15 UVA and UVB sunscreen protection is recommended to be applied to exposed skin areas before going outdoors. Guidelines for grading and management of dermatologic AEs of all severities are provided ([Appendix 10](#)).

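### Antibiotic premedication for skin toxicity, probably decided after randomisation and mostly in Arm A, is not a valid subgroup factor or stepwise covariate in the supplementary and exploratory survival analyses

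*Protocol*

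**What the plan says.** Protocol Section 10.1.2.4.2.1 gives the purpose of the subgroups: "OS subgroup analyses are planned to further explore the homogeneity of the treatment effect across participant subsets". The list ends with "Premedication with antibiotics for skin toxicity (yes, no". A Cox model with treatment arm as predictor "will be fitted separately for each subgroup category". Sections 10.1.2.4.2.2 and 10.1.2.4.2.4 apply the same subgroups to OS in the triple-negative population and to PFS.

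The exploratory analysis in Section 10.1.2.4.2.1 repeats the factor as a model candidate: "Treatment will be included in the model and a stepwise selection process" is applied, with entry at p < 0.15 and retention at p < 0.10.

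On the premedication itself:
- Section 6.1.2, headed "Premedication before futuximab/modotuximab administration", contains the skin-toxicity subsection 6.1.2.2. Only Arm A of the Randomised part receives that drug.
- Section 6.1.2.2 states: "Management of skin toxicity will be done throughout the study according to the investigator's discretion". Section 4.3 says the study is open label.
- Section 4.1.1 states: "The participants should receive the first dose of first IMP (Day 1 of Cycle 1) within 3 days after inclusion", and the sentence goes on to set the same limit after randomisation.

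No section defines the factor's time window, the qualifying antibiotics, or whether treatment of an established rash counts alongside prophylaxis.

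**The concern.** Every other item on the list reads as a characteristic present at or before entry: performance status, mutation status, prior therapy, tumour location, age, race and so on. This one describes care given around or after the first dose of the experimental drug.

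It also separates the arms. Section 2.8 notes "Neither dermatological toxicity, nor hypomagnesemia are reported as common toxicities of single-agent trifluridine/tipiracil", Section 2.5 expects no dermatological events on the control drug, and Section 8.2.5 schedules the extra dermatologic examinations for antibody-treated participants only. The 'yes' category could then be nearly all Arm A, and the 'no' category would compare nearly all of Arm B with a selected part of Arm A.

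Selection matters because Section 2.2.2 says cutaneous events are associated with responsiveness to anti-EGFR therapy. If antibiotic use tracks skin events, splitting on it may sort Arm A by response or prognosis and leave Arm B unsorted. Neither category then keeps the balance that randomisation provides, and a stepwise model that admits the factor passes the same distortion to its treatment coefficient.

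**Working it through.** **Step 1. The plan's own figure.** Section 10.2 gives 383 OS events for 90% power at HR 0.71, one-sided alpha 0.025, 1:1 allocation.
- Fixed-design events (Schoenfeld): 4 × (1.960 + 1.282)² / (ln 0.71)² = 4 × 10.51 / 0.1173, giving 359.
- Fixed-design power at 383 events: Φ(√383/2 × 0.3425 − 1.960) = Φ(1.391) = 91.8%.
- With the Table (10.2) 1 boundaries at 128, 255 and 383 events and futility stops followed, simulated power is 89.7% (HR 0.71) or 90.1% (HR 8.5/12 = 0.708). One-sided alpha ignoring futility is 0.0250.

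The stated figure reproduces. The primary log-rank test and primary Cox model are stratified on the three IWRS factors and do not use antibiotic premedication, so removing it leaves these numbers unchanged.

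**Step 2. What the factor does where it is used.** The documents give no antibiotic uptake, so three pairs were assumed (Arm A / Arm B): 50% / 1%, 80% / 1% and 50% / 10%.

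Other settings were 250 per arm, exponential survival with control median 8.5 months, uniform accrual over 21 months, cut-off at 37.5 months, unmeasured prognosis with log-hazard SD 0.5, and 300 trials per scenario. Three mechanisms were tried:
- (a) use unrelated to prognosis;
- (b) use more likely in better-prognosis patients;
- (c) any use during follow-up counts, with the uptake figure taken as the probability of starting within 3 months.

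Without the factor, the average treatment HR is 1.00 under no effect and 0.74 under a conditional HR of 0.71. In the table the first HR is under no effect and the second under that effect. Counts, SE ratio and entry rate are under no effect. The SE ratio compares the treatment log-HR with and without the factor in the model.

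| Mechanism | Uptake A / B | HR with factor in model | HR in 'no' group | 'Yes' in A / B | SE ratio | Entry at p < 0.15 |
|---|---|---|---|---|---|---|
| (a) | 50% / 1% | 1.00; 0.74 | 1.00; 0.74 | 125 / 2.5 | 1.23 | 14% |
| (a) | 80% / 1% | 1.02; 0.75 | 1.01; 0.75 | 200 / 2.5 | 1.76 | 19% |
| (a) | 50% / 10% | 1.00; 0.74 | 1.00; 0.74 | 125 / 25 | 1.12 | 13% |
| (b) | 50% / 1% | 1.20; 0.89 | 1.20; 0.89 | 125 / 4 | 1.19 | 90% |
| (b) | 80% / 1% | 1.35; 0.99 | 1.34; 0.99 | 191 / 4 | 1.56 | 84% |
| (b) | 50% / 10% | 1.15; 0.85 | 1.14; 0.84 | 125 / 33 | 1.09 | 98% |
| (c) | 50% / 1% | 3.92; 3.47 | 3.69; 3.38 | 181 / 9 | 1.60 | 100% |
| (c) | 80% / 1% | 7.45; 6.59 | 7.29; 6.98 | 214 / 9 | 2.13 | 100% |
| (c) | 50% / 10% | 2.26; 1.80 | 2.75; 2.51 | 181 / 71 | 1.25 | 100% |

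**Step 3. Reading it.**
- Under (a) there is no material bias. At 1% use in Arm B the 'yes' group has two or three controls and its HR is practically not estimable. The 'no' group keeps only 250 − 200 = 50 to 250 − 125 = 125 Arm A patients.
- Under (b) a null effect looks harmful, with two-sided 5% rejection in 21-54% of trials, and a real effect shrinks. The opposite link with prognosis would pull the other way.
- Under (c) the 'no' group in Arm A is enriched for patients who died before they could start an antibiotic, which is immortal-time bias.

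The entry rate was checked in a model with treatment and this factor only, not in the full stepwise procedure.

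**The case against.** The strongest reply is that the item says premedication, which Section 6.1.2.2 treats apart from the graded rash treatment in Appendix 10. Prophylaxis fixed at the first dose, within 3 days of randomisation, would involve almost no immortal time. This stands: immortal-time bias applies only if the factor is coded as any use during follow-up, and the protocol does not say that it is. The missing definition does not exclude that coding either.

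Second, Section 10.1.2.4.2.1 makes the subgroups conditional on sample size. That could remove a 'yes' group with hardly any controls. It does not remove the 'no' group or the stepwise candidate.

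Third, a reader might take the dermatologic event rates in Section 2.2.2 (92.9% on this regimen, 10.3% on control) as antibiotic uptake, and conclude that at most 0.103 × 250 = 26 controls and a majority of Arm A would be 'yes', making the factor nearly a copy of the arm. The documents do not support this. Event incidence is not antibiotic premedication. That control arm received capecitabine, 5-FU or best supportive care, not trifluridine/tipiracil. The only specific measure Section 6.1.2.2 recommends is sunscreen. So 26 is not a bound, and Arm A uptake is unknown.

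**Conclusion.** The point holds for the supplementary subgroup hazard ratios (OS in the double- and triple-negative populations, and PFS) and for the treatment coefficient of the exploratory stepwise model if the factor enters. Those estimates would be imprecise if antibiotic use is unrelated to prognosis, biased if it is related, and subject to immortal-time bias under any-use coding. The sizes above illustrate assumed uptake and mechanisms; they are not predictions. That the factor is set after randomisation and mostly in Arm A is a well-supported inference, not something the protocol states.

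A reader might infer that the trial's treatment effect is biased. It is not: the primary test, primary hazard ratio, 383 events, power and alpha do not depend on this factor. The practical reach is also small. SAP Section 1 records that the Randomised part was cancelled and SAP Section 2.3 marks subgroups as not applicable, so none of these analyses is planned to run. What remains is a minor correction to the protocol text.

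**What to change.** Delete the factor from the subgroup list and from the stepwise candidate list in Protocol Section 10.1.2.4.2.1; the triple-negative and PFS subgroups follow by reference. Alternatively, keep it but define it as antibiotic use for skin toxicity recorded before randomisation. Section 6.3 already collects medications from consent, so this needs no new data, although such use may be too rare to analyse.

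If on-study antibiotic use is of interest, summarise it descriptively within Arm A as safety information, without a treatment hazard ratio.

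The cost is one item in two lists. Sample size, event count, power and alpha do not change.
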